10.1.3 Analyses of Time-to-Event Variables

Time-to-event analysis will be done for RZB_75, RZB_150, PBO treatment arms for Part A, and all RZB_75/ RZB_75, RZB_150/ RZB_150 treatment arms for the entire study.

For the time to first achievement of Endpoint, the time to event will be calculated as:

- Time to first achievement (with observed event) = [date of first achievement] – [date of first study drug] + 1
- If a subject never attains an endpoint, then that subject's time to first achievement will be censored at the last visit where variable was measured. Censoring will be done within Part A for the analyses in Part A, and over the entire study for cross-period analyses. For example, if the first time a PASI 90 response is achieved in Part B, then PASI 90 will be censored for Part A analysis only.

Time to loss of response will be evaluated from the time of achievement of the same endpoint, and defined using the following algorithm:

- Never attains Endpoint (Failure at time 0)
- After achieving Endpoint, subjects will be considered loss of response if they subsequently lost the response or discontinue from the study due to AE of "Worsening of disease under study."
- Subjects will be censored at their last assessment if they do not lose the endpoint or discontinue from the study due to reasons other than AE of "Worsening of disease under study." Time to failure will be calculated starting from date of first achievement of the endpoint.

Time to event will be analyzed using Kaplan-Meier estimates for each treatment group. Treatments comparisons will be performed using stratified Log-rank test.

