4.2 OTHER TREATMENTS, EMERGENCY PROCEDURES, RESTRICTIONS

4.2.1 Other treatments and emergency procedures

There are no special emergency procedures to be followed.

Stable doses of concomitant therapies for chronic conditions, for which neither the condition nor the treatment are judged to exclude the patient from participation (See [Section 3.3](#)) are permissible. All concomitant medications should be carefully evaluated by the investigator and the CML should be contacted when there are questions regarding concomitant medications.

In the event that a patient experiences an intolerable increase of psoriasis, as deemed by the investigator, during the course of the trial the patient will be discontinued from the trial to receive rescue treatment.

In case of AEs in need of treatment symptomatic therapy according to investigator judgment will be permitted. All concomitant and/or rescue therapies will be recorded on the appropriate pages of the eCRF.

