7.3.3 Further endpoint analyses

Change from baseline in PSS at Week 16 will be analysed by the van Elteren test between the BI 655066 arm and placebo arm. The other further endpoints will be summarised descriptively, with number and proportion of responders for dichotomous endpoints and mean, median, SD and IQR presented for continuous variables.

Time to onset of *Endpoint*, the time to event will be calculated as:

- Time to first onset (with observed event) = [date of first onset] – [date of first active treatment] + 1
- If a patient never attains *Endpoint* (e.g., PASI75 or PASI90), then that patient's time to first onset will be censored at the last visit where the *Endpoint* was measured (e.g., PASI).

Time to Loss of *Endpoint* (from time of randomisation), defined using the following algorithm:

- a) Never attains *Endpoint* (Failure at time 0)
- b) After achieving *Endpoint*, patient will be a failure if they subsequently do not achieve *Endpoint* and either discontinue from the study or switch therapy

while still not achieving *Endpoint*. Time to failure will be calculated using date of first failure to achieve *Endpoint*.

- c) Patients randomised to placebo will have Week 16 (i.e. when they begin taking BI 655066) as Day 0 for determining Time to Loss of response.
- d) Patients who maintain *Endpoint* throughout the study will be censored at their last measurement

Time to Loss of *Endpoint* (from time of achieving *Endpoint* or from specific point in time) will be defined as above but only for those patients that have achieved *Endpoint*.

All Time to Event endpoints will be presented using Kaplan-Meier curves.

As sensitivity analysis, the primary and secondary endpoints will be analysed in the same way based on PP Population.

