10.1.4 Missing Data Imputations

Missing data will be imputed using the following methods for the efficacy analyses:

- Non-Responder Imputation (NRI): The NRI analysis will categorize any subject who has missing value at a specific visit as non-responder for that visit. The only exception is when if the subject is a responder both before and after this specific visit window, then the subject will be categorized as a responder for the visit. The NRI will be the primary approach in the analysis of categorical variables. Of note, this before- and after-window imputation will utilize visits across Part A and B for the risankizumab arms.
- Last Observation Carried Forward (LOCF): The LOCF analyses will use the completed evaluation from the previous visit for efficacy measures assessed to impute missing data at later visits. For observations in RZB_75/RZB_75, and RZB_150/RZB_150 arms in Part B, LOCF is continued across Part A and Part B. LOCF will be applied to the observations in PBO/RZB_75, and PBO/RZB_150 arms within the analysis period. Baseline values will not be carried forward. LOCF will be the primary approach in the analyses of continuous variables, and the secondary approach in the analyses of categorical variables.
- As-observed: The as-observed analysis will not impute values for missing evaluations, and thus a subject who does not have an evaluation on a scheduled visit will be excluded from the as observed analysis for that visit. As-observed analysis will be the secondary approach in the analysis of continuous variables.
- Multiple Imputation (MI): The MI will be used as sensitivity approach to impute missing data in primary endpoints. The variables to be included in the imputation model are listed below. If MI is not applicable due to the nature of our data (e.g., MCMC algorithm does not converge), logistic regression or mixed effect model repeat measurement (MMRM) methods will be applied as sensitivity approach, whichever applicable.

The Multiple Imputation analysis will be carried out in three steps.

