- Imputation of missing data. The imputation will be generated for each efficacy endpoint measurement. The variables to be included in the imputation model are: concomitant disease of Baseline disease severity (PASI and sPGA), Baseline weight, treatment group, Concomitant PsA at baseline (Yes: Diagnosed or Suspected; versus: No), and measurements at each visit from randomization up to the end of the analysis period. For each endpoint, 20 'complete' datasets will be generated using SAS PROC MI. The imputed post-baseline measurements will be rounded to the same precision as the observed data before the determination of responder status (e.g., PASI90).
- Analysis of imputed data sets. A CMH test, stratified by stratification factors, will be used to analyze categorical endpoints in each imputed dataset.
- Synthesis of imputation and analysis results. SAS PROC MIANALYZE will be used to generate the final inferences of the risk difference between treatment groups.

Of note, subjects who discontinued due to AE of "worsening of disease under study" will be counted as non-responders in all subsequent visits in the NRI and MI analyses, and will have their last observation prior to discontinuation carried forward in the LOCF analyses. For Observations in RZB_75/RZB_75, and RZB_150/RZB_150 arms in Part B, LOCF is continued across Part A and Part B. LOCF will not carry forward from Period A to Period B for PBO/RZB_75, and PBO/RZB_150 arms.

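### Time to first response censors patients who leave because of worsening psoriasis, although the NRI, MI and time-to-loss rules count that exit as failure; onset percentages are inflated if such exits precede later responses

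*SAP*

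**What the plan says.** SAP 10.1.3 defines time to first achievement of each PASI and sPGA response. For anyone who never attains the endpoint, "time to first achievement will be censored at the last visit where variable was measured". The reason for leaving plays no part. Protocol 7.3.3 agrees: "time to first onset will be censored at the last visit where the *Endpoint* was measured". On the estimator the SAP states: "Time to event will be analyzed using Kaplan-Meier estimates for each treatment group". It adds a test: "Treatments comparisons will be performed using stratified Log-rank test".

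Two other SAP rules do look at the reason for leaving:

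- **Time to loss of response (also SAP 10.1.3).** After attaining the endpoint, "subjects will be considered loss of response if they subsequently lost the response or discontinue from the study due to AE of" worsening of the studied disease. Patients who leave for other reasons are censored.
- **Missing data (SAP 10.1.4).** Patients who discontinue because of that adverse event "will be counted as non-responders in all subsequent visits in the NRI and MI analyses". On the standing of that method: "The NRI will be the primary approach in the analysis of categorical variables".

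The note in SAP 10.1.4 names NRI, MI and LOCF only. Nothing extends it to time to first achievement.

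Protocol 4.2.1 creates an exit of this kind. When psoriasis becomes intolerably worse, "the patient will be discontinued from the trial to receive rescue treatment".

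**The concern.** Kaplan-Meier assumes that a censored patient has the same later chance of response as those still under observation in that arm. A patient who leaves because the disease has worsened is unlikely to meet that assumption. The SAP accepts this for the same responses in its NRI and MI analyses, and for the same exit in its time-to-loss rule. For onset it treats the exit as uninformative and gives no reason.

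At stake are the onset curves for PASI 50, 75, 90 and 100 and for sPGA, and the log-rank tests, which use the same risk sets. A reader takes the height of such a curve as the share of patients who have responded by a given time. Part of that height could come from the censoring rule.

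**Working it through.** **Plan's own figures.** The documents give no figure for the time-to-event analyses. The nearest calculation is the sample size in protocol 7.7: 17 per arm for 95% power at 65% against 5%, two-sided 5%. It reproduces with a continuity-corrected two-proportion formula (14 without the correction) and is not in question. The check below takes from protocol 7.7 the 56 patients per arm and the two response rates.

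**Assumptions.** The documents give neither the number of worsening exits nor the visits at which responses first occur. Both are assumed, and no other patient is censored early.

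**Formula.** With d responders and r patients at risk at each visit, the onset percentage is 1 − S, where S = ∏(1 − d/r). If worsening leavers stay in the risk set, 1 − S is simply responders divided by 56.

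**Active arm, PASI 90 by Week 16.** First responses at Weeks 4, 8, 12 and 16 are 4, 12, 10 and 10, so 36/56 = 64.3%. With c leavers censored after Week 8, the risk set at Week 12 is 40 − c and at Week 16 it is 30 − c:

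S = (40/56) × (30 − c)/(40 − c) × (20 − c)/(30 − c) = (40/56) × (20 − c)/(40 − c)

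| Leavers c | S | Kaplan-Meier | Excess (points) |
|---|---|---|---|
| 0 | (40/56)(20/40) = 0.357 | 64.3% | 0 |
| 1 | (40/56)(19/39) = 0.348 | 65.2% | 0.9 |
| 2 | (40/56)(18/38) = 0.338 | 66.2% | 1.9 |
| 4 | (40/56)(16/36) = 0.317 | 68.3% | 4.0 |

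**Active arm, later onset.** With 1, 6, 13 and 16 responders (again 36/56) and leavers spread over Weeks 4, 8 and 12:

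- 3 leavers (1, 1, 1): 1 − (55/56)(48/54)(34/47)(17/33) = 67.5%, excess 3.2.
- 6 leavers (2, 2, 2): 1 − (55/56)(47/53)(32/45)(14/30) = 71.1%, excess 6.8.
- 8 leavers (3, 3, 2): 1 − (55/56)(46/52)(30/43)(12/28) = 74.0%, excess 9.7.

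**Placebo arm, PASI 90.** With 3 responders (0, 0, 1, 2), 3/56 = 5.4%:

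- 3 leavers (1, 1, 1): 1 − (53/54)(50/52) = 5.6%.
- 11 leavers (4, 4, 3): 1 − (47/48)(42/44) = 6.5%.

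That is about 0.1 point per leaver.

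**Placebo arm, PASI 50.** Assume 12 responders (12/56 = 21.4%), 5 by Week 8 and 7 later, with leavers after Week 8:

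- 3 leavers: 1 − (51/56)(41/48) = 22.2%.
- 6 leavers: 1 − (51/56)(38/45) = 23.1%.

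That is about 0.3 point per leaver.

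**Boundary case.** If all leavers go after the last response, the difference is zero. With the later-onset pattern and 8 exits after Week 16, the estimate stays at 64.3%.

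**The case against.** Censoring at the last measurement is the conventional rule for time to onset, and the protocol specifies it. Keeping leavers at risk changes the quantity estimated to a cumulative incidence, and the log-rank test changes meaning with it. In the time-to-loss analysis, worsening is close to the event itself, so counting it as an event there does not by itself dictate the onset rule. Large numbers of worsening exits also look unlikely. The plan expects at least 68 patients per dose to reach one year of exposure, out of 56 + 28 = 84, so it allows for at most 16/84 = 19% attrition from all causes. Four worsening exits among 56 (7%) on active drug would be a large part of that.

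The point about size stands: the effect may be small or nil. The point about convention does not remove the inconsistency, because the SAP already counts this exit as non-response for the same PASI and sPGA responses. The protocol, moreover, sends patients out of the trial when the disease becomes intolerable.

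Four stronger readings are tempting, and the documents do not support them:

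- **That the onset curves will be too high.** This needs exits that precede later responses, and the documents give no count.
- **That the excess is larger in the arm with more exits, or that it favours risankizumab.** The excess also depends on the response rate among those who remain. Above, 3 active leavers add 3.2 points and 11 placebo leavers add about 1.2. The direction between arms is not known in advance.
- **That onset is the only analysis that does not count the exit as failure.** LOCF carries the last value forward, and the as-observed analysis drops the patient from later visits.
- **That a mismatch with NRI proves an error.** NRI gives response status at one visit, whereas onset gives ever having responded by a time. The two can differ with no dropout at all. The right comparison is the share ever attaining the endpoint.

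**Conclusion.** The inconsistency is real and the direction within an arm is certain. The onset percentage is never below the figure with worsening leavers kept as non-achievers, and it is above that figure once a response follows such an exit. The excess grows with both the number of exits and the response rate among those who remain. In the active-arm examples it is roughly 1 point per leaver out of 56. In the placebo examples it is 0.1 to 0.3 point. With no such exit before a later response it is zero.

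These sizes rest on assumed response patterns and assumed numbers of leavers. They also suppose that patients who leave under protocol 4.2.1 are recorded under the adverse-event category that the SAP uses, which the documents do not state.

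The endpoints are listed as further endpoints in protocol 5.1.3 and as exploratory in SAP 10.3.1. The primary PASI 90 comparison and its alpha control are untouched. This is a worthwhile correction of low priority.

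**What to change.** In SAP 10.1.3, for time to first achievement, keep patients who discontinue because of the adverse event of worsening disease in the risk set as non-achievers. Censor them at the last scheduled visit of the analysis period: Week 16 for Part A, Week 52 for the entire study. Leave all other leavers censored at their last measured visit. Reporting a cumulative incidence with this exit as a competing event serves the same purpose, and gives the same percentage when nobody else is censored early. Record the departure from protocol 7.3.3 in SAP 14.1. Settle it before the Week 28 analysis is unblinded, since SAP 10.1 makes that the final analysis of Part A.

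The cost is one SAP sentence, one line in the censoring derivation and the entry in 14.1. Onset percentages will be slightly lower where such exits occur. The log-rank comparison will refer to response with this exit counted as failure, which the table footnotes should say. Other early leavers remain censored, so the curve can still lie above the crude share of randomised patients who responded.

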Table 4.
Visit Windows for Analysis of ECG in Part A (Safety Population)

Window Label	Target Day	Interval
Baseline	1	≤ 1
Week 4	29	[2, 71]
Week 16	113	[72, 155*]

Rx Day calculated relative to first dose date of study drug.

* The minimum of upper bound, the first dose date in Part B, and the last dose + 105 days.

Table 5. Visit Windows for Analysis of sPGA, PSS, DLQI, HAQ-DI, Pain VAS, Investigator's Global Assessment VAS, Patient's Global Assessment VAS, CRP as an ACR 20 Component, SJC, and TJC in Part A (ITT Population)

Window Label	Target Day	Interval
Baseline	1	≤ 1
Week 16	113	[2, 225*]

Rx Day calculated relative to first dose date of study drug. For subjects randomized but not dosed, Rx Day calculated relative to Randomization.

* The minimum of upper bound and the day of the first dose date in Part B.

Table 6. Visit Windows for Analysis of PASI, Vital Signs, and Local Tolerability in Part B (ITT/Safety Population)

Window Label	Target Day	Interval
Entry of Part B	1	$\leq 1^a$
Week 22	43	[2, 64]
Week 28	85	[65, 106]
Week 34	127	[107, 148]
Week 40	169	[149, 190]
Week 46	211	[191, 232]
Week 52	253	[233, 267]
Week 56	281	[268, 295 ^b]

Rx Day calculated relative to the first dose date on or after Week 16 for PBO/RZB_75 and PBO/RZB_150 arms, and relative to the date of Week 16 visit for RZB_75/RZB_75 and RZB_150/RZB_150 arms. PASI only evaluated from Week 22 to 52. Local tolerability only evaluated from Week 22 to 40.

a. If time is collected for vital sign, restrict to records prior to the first dose of study drug in Part B.

b. The minimum of upper bound and 105 days after the last dose.

Subjects who enter the Open Label Extension Study 1311.31 will not have Week 56 evaluations.

Table 7. Visit Windows for Analysis of sPGA, PSS, DLQI, HAQ-DI, Pain VAS, Investigator's Global Assessment VAS, Patient's Global Assessment VAS, SJC, TJC, Laboratory Tests, and ECG in Part B (ITT/Safety Population)

Window Label	Target Day	Interval
Entry of Part B	1	≤ 1
Week 28	85	[2, 127]
Week 40	169	[128, 211]
Week 52	253	[212, 294 ^a]

Rx Day calculated relative to the first dose date on or after Week 16 for PBO/RZB_75 and PBO/RZB_150 arms, and relative to the date of Week 16 visit for RZB_75/RZB_75 and RZB_150/RZB_150 arms.

a. The minimum of upper bound and 105 days after the last dose.

Table 8. Visit Windows for Summary of Study Drug Injections in Part A

Window Label	Target Day	Time Window
Week 0	1	≤ 1
Week 4	29	[2, 57 ^a]

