10.3.1 Further Efficacy Analysis

Further exploratory endpoints below will be analyzed among the ITT Population at all visits collected:

- Achievement of PASI 50/75/90/100
- Achievement of sPGA of clear and sPGA of clear or almost clear
- Time until the first achievement of PASI 50, PASI 75, PASI 90, PASI 100, sPGA of clear and sPGA of clear or almost clear
- Time until loss of PASI 75, PASI 90, PASI 100, sPGA of clear and sPGA of clear or almost clear response
- Change from baseline in PASI score
- Percent change from baseline in PASI
- Achievement of absolute PASI of < 3
- Change from baseline in psoriasis symptoms evaluated using the total score on the Psoriasis Symptoms Scale (PSS)
- Achievement of a Dermatology Life Quality Index (DLQI) score of 0 or 1
- Achievement of total score on the PSS of 0
- Change from baseline in DLQI
- Change from baseline in HAQ-DI, among subjects with confirmed diagnosis of PsA using CASPAR criteria and with baseline total TJC and SJC counts ≥ 3 at selected study sites
- Change from baseline in Pain VAS, among subjects with confirmed diagnosis of PsA using CASPAR criteria and with baseline total TJC and SJC counts ≥ 3 at selected study sites

- Change from baseline in Patient's Global Assessment VAS, among subjects with confirmed diagnosis of PsA using CASPAR criteria and with baseline total TJC and SJC counts ≥ 3 at selected study sites
- Change from baseline in Investigator's Global Assessment VAS, among subjects with confirmed diagnosis of PsA using CASPAR criteria and with baseline total TJC and SJC counts ≥ 3 at selected study sites
- Achievement of an ACR 20, among subjects with confirmed diagnosis of PsA using CASPAR criteria and with baseline total TJC and SJC counts ≥ 3 at selected study sites
- Investigator's global assessment among subjects with confirmed diagnosis of PsA using CASPAR criteria and with baseline total TJC and SJC counts ≥ 3 at selected study sites
- Change from baseline in CRP, among subjects with confirmed diagnosis of PsA using CASPAR criteria and with baseline total TJC and SJC counts ≥ 3 at selected study sites
- Change from baseline in TJC and SJC, among subjects with confirmed diagnosis of PsA using CASPAR criteria and with baseline total TJC and SJC counts ≥ 3 at selected study sites

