In addition, the proportion of subjects achieving PASI 90, PASI 100, sPGA of clear, and sPGA of clear or almost clear at each visit in Part B will be summarized among those who had PASI 90, PASI 100, sPGA of clear, and sPGA of clear or almost clear, respectively, at the entry of Part B.

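### SAP time to loss of response is timed from first achievement but counts subjects who never achieved the endpoint as losses at time 0

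*SAP*

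**What the plan says.** **Protocol 7.3.3** defines two measures.

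- The first runs from randomisation, with Week 16 as day 0 for patients randomised to placebo. A patient who never attains the endpoint fails at time 0.
- The second runs from achievement, or from a specific point in time. It "will be defined as above but only for those patients that have achieved" the endpoint.

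The Protocol asks for Kaplan-Meier curves and names no test for them.

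**SAP 10.1.3** defines one measure. It gives the time origin twice: "Time to loss of response will be evaluated from the time of achievement of the same endpoint", and later "Time to failure will be calculated starting from date of first achievement of the endpoint". The first rule of the algorithm is nevertheless "Never attains Endpoint (Failure at time 0", followed by a closing bracket. The section adds a stratified log-rank test. It lists the two risankizumab arms and placebo for Part A, and the two risankizumab arms for the entire study.

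**SAP 10.3.1** sets the population without limiting it to achievers: "Further exploratory endpoints below will be analyzed among the ITT Population at all visits collected". The same section also plans a by-visit summary in Part B, in which the proportion responding "will be summarized among those who had PASI 90, PASI 100, sPGA of clear" or clear/almost clear at entry to Part B.

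**The concern.** A reader takes a loss-of-response curve timed from achievement as durability among responders, and expects it to start at 100%. Under the SAP rule it starts at the share of subjects who ever achieved the endpoint.

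Counting non-achievers as failures is legitimate in a composite timed from randomisation, and the Protocol does so on purpose. The fault is to give that composite a from-achievement label and to leave out the achievers-only version. A never-achiever also has no achievement date from which to start the clock.

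Three comparisons are affected:

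- **Risankizumab against placebo, Part A.** The result is dominated by non-response.
- **sPGA, Part A.** SAP Table 5 has a single post-baseline window, so nobody can be seen to achieve and then lose the endpoint. Apart from discontinuations for worsening disease, every counted loss is a non-response.
- **Dose against dose, entire study.** The SAP does not name this comparison. It follows because only the two risankizumab arms remain. The log-rank test there combines a difference in response rate with a difference in durability.

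**Working it through.** **Inputs.** Protocol 7.7 gives 56 patients per arm and Week 16 PASI 90 planning rates of 65% and 5%. As a check on those rates, its 17 per arm for 95% power reproduces:

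- Uncorrected: (1.960·√(2·0.35·0.65) + 1.645·√(0.65·0.35 + 0.05·0.95))² / 0.60² = 13.26, so 14.
- Continuity-corrected: (13.26/4)·(1 + √(1 + 4/(13.26·0.60)))² = 16.4, so 17.

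The documents give no ever-achieved or loss rates. All such rates below are assumptions, with ranges.

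**Structure.** Let *a* be the share who ever achieve and *q* the share of achievers who later lose response, ignoring censoring.

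| | Start of curve | Later |
|---|---|---|
| SAP rule | a | a(1 − q) |
| Achievers only | 1 | 1 − q |

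**Step 1. Against placebo in Part A, with no true loss at all.** Use the planning rates as ever-achieved rates.

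- Events at time 0: 56 − 36 = 20 on risankizumab and 56 − 3 = 53 on placebo, 73 in total.
- Expected per arm: 73/2 = 36.5. Absolute difference from observed: 16.5.
- Variance: 73 × 0.25 × (112 − 73)/111 = 6.41.
- Chi-square: 16.5²/6.41 = 42.5, p = 7.2 × 10⁻¹¹.

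Over ever-achieved rates of 65–85% active and 5–15% placebo, time-0 events are 8–20 against 48–53. Chi-square runs from 29.1 (20 against 48) to 72.3 (8 against 53).

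**Step 2. One risankizumab arm**, *a* = 65–85%, *q* = 5–20%.

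- Share of counted events that are non-response, (1 − a)/((1 − a) + aq): 0.35/(0.35 + 0.0325) = 0.915 at one end and 0.15/(0.15 + 0.17) = 0.469 at the other.
- Shown as maintained, a(1 − q): from 0.65 × 0.80 = 0.52 to 0.85 × 0.95 = 0.81. Among achievers it is 0.80 to 0.95.

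**Step 3. Dose against dose.** Simulation with 4,000 runs per setting, 56 per arm, geometric loss over six visits (the PASI visits from Week 22 to Week 52) and an unstratified log-rank test at two-sided 0.05. The Monte Carlo standard error is at most about 0.8 percentage points.

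| Assumed loss | Ever achieved | Rejects, SAP rule | Rejects, achievers only |
|---|---|---|---|
| 5% vs 12% per visit | 65% both | 40% | 68% |
| 5% vs 12% per visit | 75% both | 50% | 73% |
| 5% vs 12% per visit | 85% both | 64% | 79% |
| 5% per visit, both | 65% vs 80% | 26% | 5% |

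Per-visit losses of 5% and 12% accumulate to 1 − 0.95⁶ = 26% and 1 − 0.88⁶ = 54%, outside the range used in step 2. With cumulative losses of 5% against 20%, the rejection rates are 16–32% under the SAP rule and 50–64% among achievers. The dilution is larger.

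**The case against.** The strongest defence is that the SAP rule is a coherent all-randomised measure: duration of first response, set to zero for subjects who never respond. The amendment log ties the changed definition of loss to the ITT principle, and SAP 10.3.1 uses the ITT Population. After time 0 only achievers remain at risk, so dividing the curve by its starting value recovers the achievers-only curve. Time to first achievement is reported separately, the Week 52 secondary endpoints describe maintenance, and the Part B summary among responders covers much of durability. The endpoint is exploratory. The achievers-only version gives up the randomised comparison and says little against placebo in Part A.

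Much of this limits the consequences. Zero duration can be defined, and a careful reader can rescale the curve. But the SAP does not call its measure duration of response with zeros, and the amended Protocol still keeps a separate achievers-only version. Rescaling the curve does not repair the log-rank p-value. The Part B summary omits PASI 75 and is not time-to-event.

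The dose-against-dose comparison is inferred, six visits fit PASI but not sPGA (three Part B windows in SAP Table 7), and 65% against 80% is a hypothetical contrast. The direction follows from the structure; the simulated percentages are illustrations.

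**Conclusion.** The concern holds. SAP 10.1.3 contradicts the Protocol's from-achievement definition, and nothing elsewhere in the SAP repairs it. Followed as written, it produces curves and p-values that mix non-response with loss under a label that promises loss among responders.

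The structural result needs no assumed rates: ignoring censoring, the SAP curve is the achievers-only curve multiplied by the share who ever achieved. How far that matters depends on the assumed rates. Across the stated ranges, never-achievers make up 47–91% of counted events in a risankizumab arm. The simulations ignore strata, whose sizes are not given, although the SAP test is stratified.

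The stakes are limited. The primary endpoint, its alpha, the sample size and the secondary endpoints are unaffected.

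**What to change.** In SAP 10.1.3:

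1. For the from-achievement analysis, delete the time-0 failure rule and restrict the analysis to subjects who achieved the endpoint, as in Protocol 7.3.3. State this as an exception to the ITT wording in SAP 10.3.1.
2. Present it as descriptive Kaplan-Meier curves. Give no confirmatory reading to any log-rank p-value, against placebo or between doses, because achievers are selected after randomisation.
3. If the all-randomised version is wanted, present it separately with time from randomisation, labelled as a composite of non-response and loss.

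The cost is SAP wording and reprogramming of these exploratory outputs, with no change to data collection. The achievers-only curves lose the randomised comparison, and in Part A few placebo subjects would contribute: about 3 of 56 at the planning rate (56 × 0.05 = 2.8).
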